5.2 ANALYTICAL APPROACH

Descriptive statistics will be used to summarise participant characteristics separately for each study setting, including household-level characteristics (e.g. socioeconomic status, household construction, number of household members), index-case level characteristics (e.g. age, sex) and child-level characteristics. The analyses for each endpoint will be conducted separately for each setting.

CORE STUDY

Comparison of aTB and control households: For the primary analysis, we will use random-effects logistic regression with a fixed effect for exposure group (aTB vs control) and a random intercept for household. Since control houses will be selected from the same neighbourhood as the aTB index cases, we will also include a random effect for matched set. From the fitted model, we will estimate the marginal risk difference in the proportion IGRA positive between the two groups.

Matching on neighbourhood will provide some control of confounding by neighbourhood-level factors (e.g. socioeconomic status, background exposure in the community). However, we will also conduct multivariable analyses, explicitly controlling for confounding using child-level (e.g. age, sex and degree of contact with index, such as sleeping in same room etc) and household-level covariates (e.g. household crowding). Covariate adjustment will be guided by theoretical causal diagrams, defined *a priori*.

Comparison of aTB and sTB households: For the primary analysis, we will use random-effects logistic regression with a fixed effect for TB exposure group (aTB vs sTB) and a random intercept for household. The marginal risk ratio will be estimated from the fitted model.

We will also conduct multivariable analyses, controlling for confounding using child-level, index case-level (age, sex, HIV status) and household-level covariates, as described above, with covariate adjustment guided by theoretical causal diagrams, defined *a priori*. If there is evidence of a difference in the infectiousness of aTB compared with sTB we will explore whether this is mediated through characteristics of index case disease severity (bacillary burden, cavitation etc) or other mechanisms.

Sensitivity analyses: In a high TB incidence setting, IGRA positivity in household members may be result of contact with infected individuals outside the household, rather than with the index case. This would lead to outcome misclassification since the assumption underlying our analysis is that IGRA-positivity is

a result of exposure to the index case. This effect should be non-differential so would bias estimates towards the null. We will conduct sensitivity analyses restricted to younger children (e.g. aged <10 years), with the assumption that younger children are more likely to have been infected by the household index case than through community or non-household contact. Additionally, quantitative bias analyses will be performed using alternate definitions of 'asymptomatic' and 'symptomatic' TB-C index cases to account for 'misclassification' between these groups based on discrepancies between W4SS status at screening and the additional blinded symptom data collected at Visit 1.1.

CASE CONTROL STUDY (SUB-STUDY 1)

We will assess the performance of the standard and novel tools for diagnosing aTB-C and sTB-C by calculating the sensitivity, specificity, PPV, NPV and yield, and 95% confidence intervals, of each tool. We will use ROC curves and Chi-squared tests to explore the association of tool performance with child household contact IGRA positivity, to assess the ability of these tools to identify individuals with aTB who contribute to Mtb transmission.

We will compare bioaerosol status between aTB and sTB index cases and controls. Bioaerosol measurements will also be compared with tongue swab NAAT results. We will also explore their association with child IGRA positivity, to assess their performance as a surrogate for Mtb household transmission.

TB UNCONFIRMED (TB-U)COHORT STUDY (SUB-STUDY 2)

We will use survival analysis methods to estimate the time to progression. The primary progression endpoint will be defined as a positive sputum test. An alternative progression endpoint will include worsening of symptoms or clinical status, radiological progression and/or starting TB treatment. Person-time will be calculated from date of entry to the TB-U cohort until the earliest of date of the progression endpoint, the last visit seen, or death. Participants who have not met the progression endpoint by the end of follow-up will be censored administratively at the date of the 12-month visit. Since we expect <15% to progress (based on published data), we will use restricted mean survival time (RMST) to estimate the average survival over follow-up. We will use linear regression to compare log-transformed plasma biomarkers between progressors and non-progressors, assuming a normal distribution, or Wilcoxon rank sum tests if data are non-normally distributed. Biomarkers that are measured as binary variables will be compared between groups using Chi-squared tests. Factors associated with time to progression will be explored using Cox regression.

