Cross-sectional study of Household Mtb infection (core study)	
Community screening: Adolescents and adults (≥ 15 years) who reside in households located within the study areas in each setting
 
Child contacts: Children (2-14 years) who are household contacts of people with sTB-C, people with aTB-C or of randomly selected adults in households without TB
	
1. Adolescent/Adult participants for community screening
 
Inclusion criteria:
 
 1. Age ≥ 15 years 2. Residence in the designated study area 3. Residence in a household with children (2-14 years) 
Exclusion criteria:
 
 1. Unable or unwilling to consent (>18 years) 2. Unable to unwilling to assent (15-17 years) 3. Parent or guardian unwilling to consent (15-17 years) 4. Residence in a household with a participant in a TB vaccine trial (currently or previous 2 years) 
2. Child household contacts
 
Inclusion criteria:
 
 1. Age 2-14 years 2. Household residence with an adolescent/adult participant with: 
 a. aTB-C, or b. sTB-C, or c. an adolescent/adult participant who has been selected as a healthy control (no TB) 
Exclusion criteria:
 
 1. Unable or unwilling to assent (≥ 7 years) 2. Parent/guardian unable or unwilling to consent 3. Residence in household in which any resident has been diagnosed with TB within the past 2 years 4. Residence in a household with more than one adolescent/adult with current co-prevalent TB-C
Case-control phenotyping study (sub-study 1)	Adolescents and adults (≥ 15 years) who participated in cross-sectional study of household Mtb infection (core study)	
1. Participants with aTB-C
 
Inclusion criteria:
 
 1. Adolescent/adult participant in TB screening 2. Screening W4SS negative 3. Screening sputum Xpert positive (any grade) OR Mtb MGIT positive* OR tongue swab NAAT positive 
2. Participants with sTB-C
 
Inclusion criteria:
 
 1. Adolescent/adult participant in TB screening 2. Screening W4SS positive 3. Screening sputum Xpert positive (any grade) OR Mtb MGIT positive* OR tongue swab NAAT positive

Study	Study Population	Eligibility Criteria

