3.4 STUDY SCHEDULE

A summary of study visits is provided in **Table 2**, and the flowchart of Schedule of Procedures is presented in **Appendix C**.

Table 2: Schedule of study procedures for participants enrolled in the asymptomatic TB transmission in Indonesia and South Africa study

Cross-sectional study of Household Mtb	
Visit 0: Household identification and consent
 
 • Identify geospatial areas for enumeration • Informed consent by household head • Minimal Household enumeration to determine eligibility • Dwelling/House description data
--	--

infection (core study)	
Visit 1: Screening and enrolment
 
 • Consent and enrolment of all adolescents and adults HH members • Demographics • Basic Health Questionnaire • Symptom screening (including W4SS) • Minimal physical examination (weight, height) • Sputum collection for Xpert and MGIT culture • Tongue swab NAAT collection for participants unable or refuse to produce sputum[#] • Digital chest x-ray with computer aided detection (dCXR/CAD) 
Visit 2.1 and 2.2: Community or clinic IGRA measurements (weeks 0-2 and or 8-10)
 
 • Individual assent and parent/ guardian consent for child household contacts • Structured questionnaire on contact patterns with index person and detailed dwelling/House description data • Symptom screening (W4SS modified for children) • If TB symptoms, sputum collection • Weight, height, mid upper arm circumference (MUAC) • Venous blood for IGRA testing (all children at visit 2.1; at week 8-10 (visit 2.2), only repeat IGRA if visit 2.1 IGRA was negative) • Venous blood samples -for HIV^{\$}, cell-free Mtb DNA, Mtb-specific T cells and biobanking • If any symptoms or signs suggestive of TB are identified, refer to the appropriate health facility and provide support for TB investigation and treatment in accordance with national guidelines • Referral for TB preventative therapy (TPT) for all HH contacts of people with TB (visit 2.2) 
Visit 2.3: Community, clinic or telephonic review and referral (weeks 2-14), Provide IGRA status
 
 • Issue any outstanding results for adults • Follow-up on TB treatment or TPT initiation • End of study visit for cross-sectional study

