In addition, a digital chest X-ray with computer-aided detection (dCXR/CAD) will be conducted as part of the TB screening assessment. All dCXR/CAD X-Rays which are reported as suggestive of TB by the CAD software will be reviewed by a radiologist.

Within 2 weeks of the screening visit (visit 1.0), the **adolescent/adults** screened will be categorised into one of 5 screening groups ([Figure 2](#)).

- (1) **aTB-C Participant:** W4SS screening - negative; Xpert -positive (any grade) OR tongue swab-NAAT – positive; dCXR/CAD – any result
- (2) **sTB-C Participant:** W4SS screening - positive; Xpert -positive (any grade) OR tongue swab-NAAT – positive ; dCXR/CAD - any result
- (3) **aTB-U Participant:** W4SS screening - negative; Xpert -negative-OR tongue-swab NAAT – negative; dCXR/CAD – suggestive of TB
- (4) **sTB-U Participant:** W4SS screening -positive; Xpert-negative OR tongue-swab NAAT – negative; dCXR/CAD – suggestive of TB
- (5) **noTB Participant:** W4SS screening -negative; Xpert – negative OR tongue swab NAAT – negative ; dXR/CAD – normal

Adult and adolescent participants (≥15 years) will be identified ([Figure 2](#)) for potential enrolment into either the case-control phenotyping-study (Sub-study 1; aTB-C, sTB-C) or the TB-U cohort study (Sub-study 2; TB-U). For each aTB-C participant, a control participant (1:2 ratio) will be randomly selected among noTB participants within the neighbourhood (250–700 m radius depending on the population density, using GIS coordinates) of the aTB-C participant's household.

The **child household contacts (aged 2–14 years)** of those with aTB-C and their controls, and sTB-C will be eligible for inclusion in the cross-sectional study (IGRA assessments) of household Mtb infection (core study).

[figure not shown]

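### The supporting aTB versus control model names contact with the index as a confounder, but the control index has no TB; depending on its distribution or coding, this covariate can distort the adjusted risk difference

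*Protocol*

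**What the plan says.** Protocol section 5.2 sets the primary aTB-control analysis as "random-effects logistic regression with a fixed effect for exposure group (aTB vs control) and a random intercept for household", plus a random effect for matched set. From it, "we will estimate the marginal risk difference in the proportion IGRA positive between the two groups".

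The section then says that matching on neighbourhood controls only part of the confounding and that "we will also conduct multivariable analyses, explicitly controlling for confounding". The covariates named for this are "child-level (e.g. age, sex and degree of contact with index, such as sleeping in same room etc", together with household factors such as crowding. The safeguard is the next sentence: "Covariate adjustment will be guided by theoretical causal diagrams, defined" a priori. The diagrams are not shown.

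Who the index is in a control household follows from sections 3.3 and 3.5. Table 1 admits children living with "an adolescent/adult participant who has been selected as a healthy control (no TB", and that adult "will be randomly selected among noTB participants within the neighbourhood" of the aTB-C household. The sample size entry of the protocol summary counts these adults among the index adults of all 600 households per setting. Table 2 lists, for the child visits, a "Structured questionnaire on contact patterns with index person" and gives no separate rule for control households.

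The aTB-sTB paragraph of section 5.2 has no child-level list of its own and refers back to the one above.

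**The concern.** A confounder must be related to exposure group and must affect the outcome other than through the exposure. Sleeping in the same room as a TB-free adult cannot cause Mtb infection. In control households, contact with the index therefore has no effect on IGRA status, except as a stand-in for the child's age or for crowding, and both are already on the list. In aTB households contact is part of the exposure itself. Section 5.1 reasons the same way when it justifies the risk difference: control children are exposed to the community, while aTB children are also exposed to an index case.

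A main-effect term gives both arms one common contact effect, although the true effect is positive in one and nil in the other. Control adults are drawn at random from noTB participants, while aTB-C adults are whoever tests positive. The two can differ in age, sex and relation to the child, and hence in room sharing. If they do, the adjusted risk difference changes for reasons other than confounding. What is at stake is the supporting estimate that readers will use to judge whether neighbourhood matching was enough.

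**Working it through.** **The plan's own figure.** The protocol gives no figure for the adjusted analysis. The nearest is Table 4: 80% power for 20% versus 32% (Bandung) and 7% versus 14% (KwaZulu-Natal, KZN), with 150 and 300 households and ICC 0.30. Two-sided alpha of 0.05 is assumed. The design effect is 1 + ((1 + CV²)m − 1) × ICC, where m is children per household.
- KZN: m = 2.5, CV² = (1.6/2.5)² = 0.41, design effect 1.76, power 79.7%.
- Bandung: m = 1.5, CV² = (0.7/1.5)² = 0.22, design effect 1.25, power 85.9%, so the stated 80% is slightly conservative.

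These concern the unadjusted comparison, and the point does not rest on them.

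**Set-up for the adjusted model.** Risks in control children come from Table 3: 7% (KZN) and 20% (Bandung), the same with or without room sharing. Everything else is assumed, because the protocol gives no contact data. Risk in aTB households with and without room sharing is 22% and 10% in KZN, and 42% and 26% in Bandung. At 40% sharing these give crude differences of 7.8 and 12.4 points, close to Table 4. Arms are weighted 1:2. The fit is large-sample and leaves out the random effects:

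logit P(IGRA+) = a + b × group + c × contact,

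standardised to the pooled contact distribution.

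**One case in full (KZN, 30% sharing in aTB, 60% in control).**
- Crude difference: 0.3 × 22 + 0.7 × 10 − 7 = 6.6 points.
- Fit: a = −2.878, b = 0.878, c = 0.452. Fitted risks with and without sharing are 17.5% and 11.9% (aTB) and 8.1% and 5.3% (control). The last two should both be 7%.
- Pooled sharing: (0.3 + 2 × 0.6)/3 = 0.50.
- Adjusted difference: 0.5 × (17.5 − 8.1) + 0.5 × (11.9 − 5.3) = 8.0 points.
- True difference at the pooled contact distribution: 0.5 × 22 + 0.5 × 10 − 7 = 9.0 points.

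**All cases (points).**

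| Sharing aTB / control | KZN crude → adjusted | Bandung crude → adjusted |
|---|---|---|
| 40% / 40% | 7.8 → 7.8 | 12.4 → 12.4 |
| 40% / 50% | 7.8 → 8.3 | 12.4 → 13.0 |
| 30% / 60% | 6.6 → 8.0 | 10.8 → 12.4 |
| 60% / 30% | 10.2 → 8.6 | 15.6 → 13.7 |
| 40% / all controls coded none | 7.8 → 3.4 | 12.4 → 6.3 |

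Standardising the 30%/60% case to aTB children instead gives 7.4 (KZN) and 12.1 (Bandung), against crude values of 6.6 and 10.8.

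**Second set of assumptions.** Hold the crude difference at Table 4's 7 and 12 points, with 40% of aTB children in close contact and their excess risk 2 to 4 times that of other aTB children.

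| Close contact in controls | KZN adjusted (crude 7.0) | Bandung adjusted (crude 12.0) |
|---|---|---|
| 40% | 7.0 | 12.0 |
| 20% | 6.5 to 6.1 | 11.2 to 10.5 |
| 60% | 7.4 to 7.8 | 12.6 to 13.2 |
| coded none | 5.3 to 3.5 | 8.8 to 5.7 |

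**Scale.** At 80% power a detectable difference is about 2.8 standard errors, so Table 4 implies about 7/2.8 = 2.5 points (KZN) and 12/2.8 = 4.3 points (Bandung). The shifts from unequal sharing are below one standard error. In the first set, the shifts from coding controls as no contact (7.8 − 3.4 = 4.4 and 12.4 − 6.3 = 6.1) are above it.

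**The case against.** Several points on the other side stand.

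- Contact appears only in the additional multivariable analysis. The list is introduced as examples, and the a priori causal diagrams are the stated means of dropping a covariate that is not a confounder.
- No sharing shares are given, so neither size nor sign can be fixed from the protocol.
- The protocol does not say that only main effects will be fitted. A model with a group-by-contact interaction would avoid forcing a common effect.
- A reader might infer that contact will be blank for controls, so that every control child drops out of the fit. The text does not support that: control households also have Visit 2.1, where the questionnaire is given, and each has a nominated index adult.

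The best technical objection is that the shift reflects a different estimand, since the adjusted model standardises to the pooled contact distribution. This stands only in part. In the unequal-sharing cases the adjusted value lies between the crude difference and the true contact-standardised one, and it equals neither (KZN 30%/60%: 6.6, 8.0, 9.0). So it does not estimate that target either. The diagrams do not settle the matter, because the text already names contact with the index as a confounder for this comparison and the diagrams would have to contradict it.

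**Conclusion.** The point holds as a minor flaw in a supporting analysis. Section 5.2 names as a confounder a variable that cannot affect infection in control households and only modifies the effect in aTB households. As a main effect it can bias the adjusted risk difference in either direction, by about 0.5 to 2 points under the assumed sharing shares. It can roughly halve the difference if control children are coded as having no contact. With equal contact distributions there is no shift.

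These sizes rest on assumed room-sharing shares and assumed risks by contact; only the control risks, the 1:2 ratio and the Table 4 differences come from the protocol.

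A reader might infer that the co-primary aTB-control result is biased or its power wrong. The protocol does not support that: the primary model contains no contact term, and Table 4 does not depend on one. Nor does the point reach the aTB-sTB comparison, where the index has TB in both arms and contact means the same thing.

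**What to change.** In section 5.2, under the aTB-control comparison, remove degree of contact with the index from the adjustment set. Adjust there only for variables that mean the same in both arms, such as the child's age and sex and household crowding. Add that contact with the index will be examined as an effect modifier or dose-response within TB households.

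Because the aTB-sTB paragraph borrows its child-level covariates from this list, restate them there so that contact with the index remains available for adjustment in that comparison.

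The cost is a sentence or two in section 5.2, carried into the SAP. No data collection, sample size or primary analysis changes. It is best done before outcome data are seen, so that dropping the covariate cannot look like a choice made on the results.

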Genotyping Mtb isolates has been utilized to study TB transmission. In a study that evaluated people with aTB and their index TB case, 7/10 people with culture-positive aTB had drug resistance similar to that of the index person and three of these were confirmed with genome sequencing⁷. The high costs of genotyping, mutation rate of Mtb and within-host variation are some of the limitations for such an approach. Although some of the Mtb transmission and new infection occurs outside the household or not from a known contact, especially in high burden settings, presence of TB infection in known contacts is still the most feasible recommended approach to estimate Mtb infection at community level. The relative ease of measuring Mtb transmission and new TB infection within a household, household TB infection prevalence and incidence, and case notification rates in children have been used to quantify population level impact²⁴.

WHO FOUR SYMPTOM SCREENING (W4SS)

The WHO-recommended four-symptom screen (W4SS) is a standardised symptom-based screening tool for TB disease. It was first recommended by WHO in 2011 to facilitate detection of TB in PLHIV and allow the safe initiation of TB preventative therapy in high-burden, low resource settings²⁵. The tool involves assessment for the presence of four key symptoms: cough, fever, night sweats and weight loss.

If any one of these symptoms is present, the individual is considered *screen-positive* and requires further TB investigation. The absence of all four symptoms is considered *screen-negative* and has been shown to have a high-negative predictive value in high-burden settings²⁵. The W4SS was originally developed as a simple rule-out tool to be used by healthcare workers for PLHIV being evaluated for isoniazid preventative therapy (IPT), now referred to as TB Preventative Therapy (TPT).

Subsequent systematic reviews have demonstrated an overall sensitivity of 83%, and a specificity of 38% for the detection of TB in PLHIV. Among outpatients not yet on antiretroviral therapy (ART), sensitivity is slightly higher (84%) with a similar specificity (37%), whereas among PLHIV already on ART, sensitivity drops to approximately 53%, with specificity increasing to 70%⁶³.

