		
3. Participants selected as healthy controls
 
Inclusion criteria
 
 1. Adolescent/adult participant in TB screening 2. Screening W4SS negative 3. Screening sputum Xpert negative; AND Mtb MGIT negative* 4. Selected as a healthy control in the Cross-sectional study of Mtb infection in households (see above) 
ALL 3 groups above
 
Exclusion criteria
 
 1. Unable or unwilling to consent 
* MGIT results returning after enrolment may result in study group re-categorisation

Cohort study (sub-study 2)	Adolescents and adults (≥ 15 years) who participated in TB screening.	
Participants who meet the study case definition for bacteriologically-unconfirmed TB (TB-U)
 
Inclusion criteria:
 
 1. Adolescent/adult participant in TB screening 2. All three sputa Xpert are negative/ ‘trace’ AND all three sputum are Mtb MGIT negative 3. Screening dCXR/CAD interpretation is “suggestive of TB” 4. Clinical assessment at phenotyping visit does not suggest a non-TB aetiology for dCXR/CAD findings and is consistent with TB-U 5. Participant did not commence TB treatment after phenotyping visit 
Exclusion criteria
 
 1. Unable or unwilling to consent to longitudinal follow-up

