3.8 STUDY OUTCOMES/ ANALYSES

The study is designed to assess both the transmission of Mtb within households and the diagnostic performance of current and novel tools for detecting asymptomatic TB. The outcomes are grouped into primary and additional outcomes categories as outlined below.

CORE STUDY

Primary endpoint: Cumulative prevalence of child household contact IGRA positivity or confirmed TB (TB-C) at 10 weeks after diagnosis of the index case.

Additional outcomes/ analyses:

- (1) Proportion of children that convert from negative IGRA status at baseline to a positive IGRA status at 10-week visit.
- (2) Proportion of children with a positive plasma cell free Mtb DNA assay and positive Mtb-specific T cell activation assay, stratified by household group.
- (3) Whole genome sequencing of Mtb isolates from people with TB-C and household contacts.

CASE-CONTROL PHENOTYPING STUDY (SUB-STUDY 1)

- (4) Sensitivity, specificity, positive predictive value, negative predictive value, yield, feasibility, acceptability of digital chest x-ray with computer aided diagnosis (dCXR/CAD), sputum Nucleic Acid Amplification Test (NAAT), Mycobacteria Growth Indicator Tube (MGIT), tongue swab NAAT, and bioaerosol collection facemask mask NAAT to detect aTB-C.
- (5) Symptoms, health outcomes quality of life, comorbidities, nutritional status, and TB history, relative to group and W4SS status at screening.

(6) Proportion and characteristics of participants with detectable exhaled breath condensate lipoarabinomannan (LAM), positive plasma cell free Mtb DNA assay, positive Mtb-specific T cell activation assay and additional blood-based TB biomarkers, stratified by group.

TB UNCONFIRMED (TB-U) COHORT (SUB-STUDY 2)

(7) Time to event and factors associated with microbiological or clinical progression in participants with initially untreated aTB-U.

(8) Plasma biomarkers (including cell free Mtb DNA, Mtb-specific T cells, transcriptional signatures) that correlate with progression from aTB-U in the 12 months after TB screening

(9) Proportion and characteristics of participants with TB screening results suggestive of (TB-U) who have a subsequent positive sputum GeneXpert Ultra, sputum MGIT, tongue swab NAAT or Bioaerosol collection facemask mask NAAT.

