Table 4: Minimum risk difference that can be detected in each site with 80% power, comparing aTB and control households

Number aTB cases	Number controls ¹	Mean children per HH	ICC	% IGRA positive in control HH	% IGRA positive in aTB HH	Risk difference ²	Power
Indonesia							
150	300	1.5	0.30	20%	32%	12%	80%
South Africa							
150	300	2.5	0.30	7%	14%	7%	80%

¹Number of control households. ²Absolute difference = proportion of children IGRA+ in aTB households minus proportion of children IGRA+ in control.

For our second co-primary objective, we have used the risk ratio (relative risk) as the effect estimate of interest, because the duration of exposure for children in aTB-C and sTB-C households is expected to be similar. For policy decisions, it would be useful to know that the transmission risk of aTB-C is not substantially lower than that of sTB-C; therefore, we have used a non-inferiority approach for our power calculations. We have assumed that the prevalence of IGRA positivity in children in sTB-C households is 40% in Bandung and 18% in KwaZulu Natal (our best estimates, based on available data). With 150 sTB-C and 150 aTB-C index cases, we will have at least 80% power in each setting to demonstrate that the transmission risk with aTB-C is not less than 50% compared with that of sTB-C, assuming that the true risk ratio (RR) is at least 0.90 ([Table 5](#)).

Table 5: Relative reduction that can be excluded with 80% power, comparing aTB and sTB households¹

Number sTB cases	Number aTB cases	% IGRA positive in sTB HH	% IGRA positive in aTB HH	Risk ratio (aTB/sTB)	Relative reduction that can be excluded ²
Indonesia - aTB vs sTB					
150	150	40%	28%	0.70	0.46
150	150	40%	32%	0.80	0.55
150	150	40%	36%	0.90	0.63
South Africa - aTB vs sTB					
150	150	18%	12.6%	0.70	0.43
150	150	18%	14.4%	0.80	0.49
150	150	18%	16.2%	0.90	0.55

¹Assuming ICC=0.30. ²Lower limit of 95% confidence interval for risk ratio

CASE-CONTROL STUDY (SUB-STUDY 1)

The case-control study will enrol 150 aTB-C and 150 sTB-C cases, and 300 community controls with no TB. Assuming that the true sensitivity and specificity of the Plus Life tongue swab and bioaerosol collection facemask diagnostic tools are between 70-95%, with 150 aTB-C and 150 sTB-C cases, we will be able to estimate the sensitivity with a precision of $\pm 7.6\%$ to $\pm 4.0\%$. With 300 controls, we will be able to estimate the specificity with a precision of $\pm 5.3\%$ to $\pm 2.6\%$.

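### Specificity, PPV and NPV are planned for sTB-C, but the only named comparator is 300 W4SS-negative controls with normal X-rays, so the result will not describe symptomatic people without TB

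*Protocol*

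**What the plan says.** Protocol section 5.2, under the case-control study, says the standard and novel "tools for diagnosing aTB-C and sTB-C by calculating the sensitivity, specificity, PPV, NPV and yield" will be assessed, with 95% confidence intervals.

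Section 3.8, outcome (4), is narrower. It lists the same measures and ends with "tongue swab NAAT, and bioaerosol collection facemask mask NAAT to detect aTB-C"; sTB-C is not mentioned. Secondary objectives 1 and 2 in section 2 likewise speak only of detecting aTB.

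Section 5.1 gives the sample: "The case-control study will enrol 150 aTB-C and 150 sTB-C cases, and 300 community controls with no TB". Sensitivity rests on the two case groups and specificity on the controls: "With 300 controls, we will be able to estimate the specificity with a precision of" ±5.3% to ±2.6%. No other non-case group is named for specificity.

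Table 1 in section 3.3 requires of controls "2. Screening W4SS negative 3. Screening sputum Xpert negative; AND Mtb MGIT negative". Section 3.5 draws them at random from noTB participants near each aTB-C household, and defines that screening group as "W4SS screening -negative; Xpert – negative OR tongue swab NAAT – negative ; dXR/CAD – normal".

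**The concern.** A person with sTB-C is W4SS-positive by definition, so a test for sTB-C has to separate TB from other causes of cough, fever, sweats or weight loss. The relevant specificity is therefore the one among W4SS-positive people who do not have TB. Followed as written, the plan compares symptomatic cases with controls chosen to have none of the four symptoms and a normal X-ray.

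False positives that arise in people with other symptomatic illness would have little chance to appear in such controls. The reported sTB-C specificity would answer a different question from the one its label suggests, and any PPV or NPV built on it would inherit the error. Reweighting to true prevalence would correct the case-to-control ratio but not the population in which specificity was measured.

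**Working it through.** **1. The plan's own precision figures.** Inputs from section 5.1: 150 cases of each type, 300 controls, true values of 70% to 95%. The half-width of the exact (Clopper-Pearson) 95% interval reproduces them:

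| Quantity | Count | Half-width | Protocol |
|---|---|---|---|
| Specificity 70% | 210/300 | 5.33% | 5.3% |
| Specificity 95% | 285/300 | 2.64% | 2.6% |
| Sensitivity 70% | 105/150 | 7.61% | 7.6% |
| Sensitivity 95% | 142/150 | 3.95% | 4.0% |

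The arithmetic is sound. The question is which population the specificity rows describe.

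**2. Who is in the specificity denominator.**
- Controls must be W4SS-negative (Table 1), so W4SS-positive controls number 0 of 300 per setting.
- Controls come only from noTB, which requires a normal dCXR/CAD (section 3.5 and the definitions tables), so no control has an X-ray suggestive of TB at screening.

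The ±5.3% to ±2.6% therefore applies to W4SS-negative, X-ray-normal adults. For W4SS-positive people without TB, the designated control group supplies no observations.

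**3. Where symptomatic people without confirmed TB appear in the study.**

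| Group | Screening dCXR/CAD, Xpert, MGIT | Novel tests at Visit 1.1 | Assigned by 5.2 to sTB-C accuracy |
|---|---|---|---|
| W4SS-positive, NAAT-negative, suggestive X-ray (sTB-U) | Planned | Yes | No |
| W4SS-positive, NAAT-negative, normal X-ray | Planned | No, unless a later positive MGIT makes them cases | No |

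Sections 3.4 and 3.5 plan sputum for Xpert and MGIT, and dCXR/CAD, for every screened adult whatever the symptoms. TB-U participants attend the same Visit 1.1 as sub-study 1. The second row fits none of the five screening groups in section 3.5.

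**4. dCXR/CAD.** The schedule in Appendix C shows no X-ray at Visit 1.1, so for controls the available X-ray is the screening one on which they were selected. Its specificity in them is at or close to 100% by selection.

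**5. PPV and NPV.** With sensitivity Se, specificity Sp and prevalence π, PPV = Se·π / [Se·π + (1 − Sp)(1 − π)]. Take Se = Sp = 0.95:
- at the 150:300 mix, π = 1/3: 0.3167 / (0.3167 + 0.0333) = 90.5%;
- at π = 0.50%: 0.00475 / (0.00475 + 0.04975) = 8.7%;
- at π = 0.25%: 0.002375 / (0.002375 + 0.049875) = 4.5%.

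The last two prevalences are the aTB figures in Table 3, used only as illustration because no sTB prevalence is given. The fixed ratio is one fault and would affect aTB-C as well. For sTB-C there is a second: even with π corrected, Sp comes from the wrong population.

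**The case against.** **A reader might infer that no symptomatic person without TB is tested, or that sTB-C specificity cannot be computed at all.** The documents do not support this. Every screened adult is to have Xpert, MGIT and dCXR/CAD, so specificity of the standard tools in symptomatic people can come from the screening data. sTB-U participants have the novel tests at Visit 1.1, where a non-TB cause may be found (Table 1). A number can also be calculated from the 300 controls; the fault is the population it describes. What remains is that section 5.2 does not assign the other data to this purpose, and that sTB-U participants all have suggestive X-rays and so are not a full symptomatic comparator.

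**A reader might also size the bias from the Background's W4SS figures**, "overall sensitivity of 83%, and a specificity of 38% for the detection of TB in PLHIV", with 37% and 70% by treatment status. One minus these gives 62%, 63% and 30% of TB-free people W4SS-positive. But those reviews cover only people living with HIV, to whom sub-study 1 is not restricted, and the share excluded says nothing about how often a tool is falsely positive in them. For tongue swabs the Background reports 100% specificity in multiple studies, so the excess may be small for some tools.

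**Controls are not necessarily free of all symptoms or lung disease.** This is right. The definitions allow a W4SS-negative person to have other TB symptoms, and a normal X-ray does not exclude all lung disease. The firm statement is only that none is W4SS-positive.

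**The choice of comparator may belong in the SAP, and one specificity shared by both case groups is a natural reading.** This has some force: the analysis is secondary and sTB-C accuracy appears in one sentence. But that sentence goes beyond outcome (4), and section 5.1 names one comparator, which does not suit it.

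**Conclusion.** The point holds in a limited form. Section 5.2 promises specificity, PPV and NPV for sTB-C, which outcome (4) does not ask for and the named controls do not support. The firm figure is 0 W4SS-positive people among 300 controls per setting. The resulting specificity applies to W4SS-negative adults with a normal X-ray.

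That it would be too high for symptomatic people without TB is a judgement. It assumes that other symptomatic illness produces at least some additional false positives. The amount will differ by tool and cannot be derived from the documents. The co-primary comparisons are not affected.

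**What to change.** In section 5.2, sub-study 1:

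1. For the novel tools, report sensitivity only for sTB-C. Limit specificity from the 300 controls to aTB-C, in line with outcome (4), and label it as applying to W4SS-negative adults with a normal X-ray.
2. For dCXR/CAD and Xpert, estimate specificity among W4SS-positive adults from the community screening data, with MGIT as reference. This covers only adults with a sputum culture result. Do not take dCXR/CAD specificity from controls selected for a normal X-ray.
3. Do not report PPV or NPV for sTB-C from the sub-study 1 sample.
4. Report any novel-test results from sTB-U participants at Visit 1.1 separately, stating that all have X-rays suggestive of TB.

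The cost is protocol and SAP wording plus one further analysis of screening data. No new participants or samples are needed. The downside is that no novel-tool specificity is reported for sTB-C.
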